## **Additional Exploratory Questions:**

Additional exploratory questions for which we will not specify hypotheses include:

- Do implementation challenges impact a clinic's ability to provide this option to DMPA users in the future?
- Are there other potential non-safety related harms associated with self-administration of DMPA sc compared to clinic administration? (e.g., forgoing other indicated health care services like STI testing in the event of a new sexual partner)
- Do satisfaction and/or continuation outcomes differ by age group or DMPA user status (i.e., continuers, first-time initiators, past users)?

#### **Previous Similar Studies**

Prior studies show that DMPA self-injection is effective, feasible, and acceptable to patients. Most recently, Beasley et al. (2014) conducted a randomized trial with 137 women to evaluate the feasibility, acceptability, and continuation of self-administration of DMPA sc versus clinical administration, and to confirm the therapeutic effect using trough serum levels. They found that 90 out of 91 women randomized to the self-administration group were able to correctly self-inject. Continuation rates were somewhat higher in the self-administration group (71% vs. 63%); however, this difference was not statistically significant (p=0.47) and the study did not have adequate statistical power to detect a difference of this magnitude (i.e., 8%). All of the women who reported continuous use of DMPA had serum levels in the therapeutic range, confirming the ability of women to learn self-administration, continue it successfully at home, and reliably self-report such use. This study required repeated visits in both groups to assess serum levels and therefore involved significant intervention with both groups, potentially attenuating the difference between groups.

A non-randomized study of 120 women by Cameron et al. (2012) found that 80% of self-injections were given on time, and that no injections were given beyond the acceptable 14-week interval. The authors also found that continuation rates were higher in the self-administration group than the clinic

administration group (88% vs. 72%); however, this difference was not statistically significant and again the study did not have statistical power to detect such a difference. Cameron et al. found that the majority of women who wanted to use Depo at home were able to do so; however, 20% experienced some difficulty with one or more of the self-injections due to either resistance to the medication passing through the needle (17%) or the needle detaching from the syringe (2%).

Prabhakaran and Sweet (2012) conducted a non-randomized pilot study to evaluate feasibility, continuation, and patient satisfaction with self-administered DMPA sc. This prospective study enrolled 50 women at Planned Parenthood health centers in Florida who were taught self-injection and provided with home injection kits. The continuation rate at one year was 74% and no pregnancies were reported. In addition, 87% reported self-injection to be "very easy" or "easy" and 94% said they would be likely to recommend self-injection to other women. The authors conclude that self-injection of DMPA is feasible, acceptable, and continuation is high.

Earlier studies confirm that women are interested in self-injection. Lakha et al. (2005) surveyed 176 women and found that two-thirds of those currently using DMPA expressed interest in self-administration. Of women who had discontinued DMPA in the past, 77% expressed interest in a method that would reduce the number of clinic visits and 40% would regain interest in DMPA if self-administration were an option. In a study of Lunelle, Stanwood et al. (2006) also concluded that self-injection is feasible and may result in greater satisfaction and contraceptive success.

Furthermore, the safety and feasibility of other self-administered subcutaneous injections is well documented with many different medications for both adults and adolescents (e.g., insulin, epinephrine, heparin, heparin, and methotrexate). Patient ability to learn how to safely perform subcutaneous injections and to do so with short (10-minute) teaching sessions has also been documented. Compliance and patient satisfaction with self-administration is similar to nurse-administered medications.

To our knowledge, only one study by Williams, Hensel, and Fortenberry (2013) examined self-administration with adolescent DMPA users (ages 14 and older) and found that the majority were interested in self-administration and nearly all were able to do so successfully with brief education and minimal assistance. We seek to ensure that this practice will be feasible and effective in real-world settings for a broader range of the patients we serve.

In sum, the findings of previous studies all point to greater continuation among DMPA self-administrators, but no studies have had sufficient statistical power to detect a clinically significant difference between self- and clinic administration. This study builds upon the strengths of prior studies to generate additional evidence on continuation and patient-centered outcomes to consider whether this practice is feasible and effective for both adult women and adolescents in Planned Parenthood settings.

#### STUDY DESIGN

This will be an open-label, randomized parallel group clinical trial to study DMPA sc self-administration at two Planned Parenthood affiliates serving diverse patient populations. A total of 400 female patients

requesting DMPA will be randomized to either self-administration of DMPA sc or clinic administration (usual care) in a 1:1 allocation. Subjects will be followed for one year to compare method continuation rates and satisfaction between arms. All subjects will receive reminders approximately two weeks before their next injection is due. Follow-up surveys will be conducted at 6 and 12 months via secure email, phone, text messaging, or a combination to increase response rate. Adherence will be monitored by subject self-report and study outcomes will be ascertained by self-report and medical record review.

We hypothesize higher continuation rates among self-administration users compared to those who receive in-clinic administration and have sufficient statistical power to detect an estimated 13% increase (80% power; one-sided  $\alpha$ =0.05, allowing for 15% loss-to-follow-up). We project a 57% one-year continuation rate among the clinic administration group based on the findings of the CHOICE Project in St. Louis, which also provided free contraception for one year and included adolescents (Peipert et al. 2011). We project a 70% continuation rate among the self-administration group based on similar studies described above (though slightly lower due to the inclusion of adolescents in our study). Given our primary research question, and that all prior studies suggest higher continuation among women self-administering DMPA, a one-tailed hypothesis test is appropriate.

The study will include minors (ages 15–17) due to exceedingly limited information available thus far, but will not oversample adolescents. The proposed trial will be substantially larger than previous studies and the first to have adequate statistical power to detect a clinically relevant and plausible difference between self-administration and usual care. To permit some assessment of generalizability of the results, we will also calculate overall DMPA continuation rates for all DMPA users at each participating health center at the end of the study period.

## **Eligibility Criteria**

The study will enroll females ages 15–44 requesting DMPA at participating health centers, including method initiators and continuers.

## **Inclusion Criteria**

- Females ages 15–44
- Current or past users of DMPA or desires initiation of DMPA for contraception
- Can understand spoken and written English or Spanish
- Willing to consider/attempt DMPA self-injection
- Willing to be randomized to either self- or clinic administration of DMPA
- Do not want to become pregnant in the next 12 months
- Willing to provide contact information and to complete three surveys at baseline, 6 months, and 12 months

5

- Have consistent access to a working telephone, email, and Internet
- No contraindications to DMPA use

### **Exclusion Criteria**

- Suspected or confirmed pregnancy
- Vaginal bleeding of unknown etiology
- Known or suspected breast cancer

- Acute liver disease
- High blood pressure (Systolic ≥ 160 mm Hg or diastolic ≥ 100 mm Hg)
- Known hypersensitivity to medroxyprogesterone acetate or any other components of DMPA
- Desire for pregnancy within one year

## **Subject Recruitment**

Recruitment will begin in July 2015 and will continue for approximately six months until a combined total of 400 subjects have been enrolled (200 intervention; 200 control). Participants will be recruited from two Planned Parenthood affiliates: Planned Parenthood Gulf Coast (Houston, TX health center) and Planned Parenthood of Central and Greater Northern New Jersey (Elizabeth, NJ and Hackensack, NJ health centers).

Patients desiring DMPA will be invited to receive more information about the study. Patients who are already using DMPA or scheduled for a DMPA injection visit will be approached by a trained Research Coordinator or approved representative. Minors will be approached with their parent or guardian if present (see consent procedures below). Patients scheduled for a DMPA injection visit may also be introduced to the study by phone prior to their appointment. Existing DMPA users may also be introduced to the study using secure existing patient communications channels such as patient portals or message retrieval systems.

At both sites, patients who desire contraception but have not yet selected a method are typically seen by a health center assistant for contraceptive counseling prior to seeing a clinician. Women who present for a new contraception consultation may be invited into the study *only after they have decided to start DMPA*. Telling them about the study earlier may make them feel pressured to use DMPA given the free contraception and compensation they would receive and reduce the generalizability of study findings. Women choosing to initiate DMPA will be approached by the Research Coordinator. This may occur in counseling or exam rooms depending on clinic flow.

The Research Coordinator or approved representative will discuss the study with potentially eligible women, briefly summarizing the study in plain language and highlighting benefits of participation (See Appendix: Recruitment Talking Points & Tips). If a woman is interested in hearing more about the study, the Research Coordinator or approved representative will screen the patient for eligibility using the Eligibility Screening Checklist form (See Appendix). Patients who are ineligible or refuse to participate once screened will be tracked by the Eligibility Screening Checklist form, which will be completed for all women who are screened regardless of whether they proceed to consent and enrollment to track refusals and reasons for ineligibility. Patients who screen eligible and are interested in participating will undergo the informed consent process.

### **Informed Consent**

The Research Coordinator or approved representative will review the appropriate consent forms with the patient. Patients should not enroll if they know they would not be interested in learning the self-administration procedure. As patient medical records may be reviewed as part of the follow up process, consent for this must be obtained. Combined Consent and HIPAA Authorization Forms will be located with the locked study materials. The Consent and HIPAA Authorization Forms (2 copies) will be reviewed

and signed after the patient has been given the chance to ask any additional questions. The person obtaining the consent will print and sign their name and fill in the date sections of the form. Patients will be offered a copy of the form.

### Consent and Assent Procedures for Minors

Houston, TX Study Site. In the state of Texas minors (<18) require parental consent to participate in research unless they are pregnant, emancipated, or living apart from their parents and managing their own affairs (and age 16+) (Tex. Fam. Code. Ann. §32.003). Therefore, minors ages 15–17 will require parental consent to enroll in the study and will also assent to participate. Parental Consent and HIPAA Authorization forms and Assent Forms of a different color will be kept with locked study materials and used only for patients ages 15–17 (See Appendix). Williams, Hensel, and Fortenberry (2013) successfully enrolled 55 adolescents (≥14) in a similar study with parental consent procedures.

Requirements for parental consent will follow both IRB requirements and site-specific procedures in compliance with the applicable laws of the jurisdiction in which the research will be conducted [45 CFR 46.402(a)]. Given the low level of risk associated with the study procedures, we will request IRB approval for the consent of *one* parent or guardian. To obtain parental consent from two parents would require significant burden on study subjects and may prove difficult or impossible for many subjects depending on their home circumstances. It would also require subjects to disclose the use of contraception to both parents, which could create an additional burden and increased discomfort for adolescent subjects. Furthermore, because minors can consent on their own to family planning services (including Depo Provera), they typically do not attend appointments with their parents. Therefore, we will request IRB approval to conduct the informed consent process by telephone with one parent or guardian with written consent provided to a secure fax line or scanned email or delivered in person by the adolescent. We will also request IRB approval to introduce the research to minors by phone prior to their visit so that they can bring a parent if feasible or otherwise prepare for the consent process.

**New Jersey Study Sites.** In the state of New Jersey, minors ages 15 and older are not restricted in their legal rights to consent to participate in research on their own. Nevertheless, these sites will follow the same procedures outlined for the Houston site above.

### Randomization and Assignment

Subjects who consent to participate will then be randomized to self-administration or standard clinic administration in a 1:1 allocation as follows. Before the study begins, the sequence for 1:1 group allocation will be predetermined stratified by study site. Separate randomization sequences will be generated for each site using randomly permuted number blocks.

Group assignments will be placed in sealed opaque envelopes and will be maintained by the Research Coordinator. The envelopes will be opened by the Research Coordinator or approved representative only after participant enrollment and informed consent. Study staff will complete and sign a Randomization Form for each randomized subject (See Appendix).

Crossover will be permitted from the self-administration arm to the clinic administration arm only. Any subject crossover will be documented by the Research Coordinator or approved representative with the subjects' ID number to permit later assessment of crossover and ITT analyses.

Due to the nature of the study, no blinding will be used.

## **Study Procedures**

Once enrolled, all participants will be seen by a clinician. Based on study assignment, subjects will either be taught to self-inject or will be administered DMPA by qualified clinic personnel. Nurses who dispense DMPA sc (regardless of study arm) will record the name of each subject receiving the medication, her chart number, and the lot number of the medication distributed to the patient on a Study Drug Distribution Log to be maintained in the pharmacy.

Subjects who are randomized to self-administration will be taught self-administration by a clinic nurse (or other qualified personnel) following an instructions sheet based on the drug packaging insert. If willing, subjects will then self-administer DMPA sc under nurse supervision. Subjects who are able to correctly self-administer DMPA sc as assessed by the supervising nurse and who are interested in continued home self-administration will then be provided medication (3 doses of DMPA sc), a self-administration kit (includes alcohol swabs, cotton pads, bandages, mini sharps disposal container), and instructions to do so for the subsequent 3 injections along with a small calendar showing the appropriate dates for injection. The calendar will also indicate when the subject will be asked to complete each of the 2 follow-up surveys.

Subjects who are uninterested in self-administration either after the educational session or after correctly self-administering medication in the office will be permitted to crossover to the clinic administration group and remain in the study. They will be re-assigned to the clinic administration group and be followed accordingly. Subjects will not be told ahead of time that they can opt out of their randomization assignment and remain in the study to discourage enrollment of subjects who are not actually willing to be in the self-administration group.

Subjects new to DMPA will be started using the QuickStart protocol (per Planned Parenthood routine practice) and will be instructed to perform a provided pregnancy test in four weeks and report the result to clinic to be documented by the Research Coordinator in the subject correspondence log. Subjects who did not provide the result of the pregnancy test will be contacted by study staff to be documented in the correspondence log.

All subjects will complete an electronic baseline survey in the clinic (using tablets provided by the study) assessing demographics, sexual activity, reproductive history, and contraceptive use and satisfaction. Subject contact information will be collected for each participant including home, work, and mobile telephone numbers; home address; e-mail; and an alternate person to contact if they cannot be reached after several attempts. This information will be used for reminders and to contact the subject for follow-up surveys at 6 and 12 months following enrollment. After completing the survey, subjects will receive a re-loadable cash card (See Compensation section below).

8

## **Follow-Up Procedures**

Subjects will either return to the enrollment clinic or perform self-injection every 12–14 weeks, depending on study arm. The appropriate date for injection will be indicated on the subject's instructions for injection/calendar. All subjects (both arms) will receive reminder emails and/or text messages two weeks *before* their next injection is due. Reminders will be generated by PPFA investigators using the secure Qualtrics electronic survey platform which enables programmable email and text message communications.

If a subject is uncertain if she was able to administer the entire dose of DMPA she should return to the enrollment clinic and have a complete dose administered. The event will be recorded and reported to the Pfizer Quality Complaints department. These subjects may continue to receive injections at the enrollment clinic or return to self-administration; this will be documented by the site Research Coordinator.

Subjects who are uncomfortable with self-injection at any point in the study may return to the enrollment clinic to receive their injection per usual clinic protocol (i.e. study arm crossover to usual care will be permitted and tracked). They will be asked to complete all surveys and follow-up activities and be included in the clinic administration group. Subjects should continue to complete all surveys regardless of the location at which she receives her injection.

Crossover will be permitted from the self-administration arm to the clinic administration arm only. Any subject crossover will be documented by the Research Coordinator with the subjects' ID number to permit later assessment of crossover and ITT analyses.

The Research Coordinator will provide the Principal Investigator with a list of subjects enrolled each month so that PPFA investigators can complete the appropriate follow up. Approximately two weeks after subjects' target injection dates, follow-up surveys will be emailed by PPFA investigators to all participants. If no survey is completed by 16 weeks after previous injection, study staff will contact the subject twice and at her alternate contact to remind them to complete the survey whether they administered DMPA or not.

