# **Objectives and Hypotheses**

The primary study objective is to compare one-year method continuation rates between patients who self-administer DMPA sc outside of the clinic setting and those who receive in-clinic administration of DMPA sc. Secondary objectives are to: confirm the feasibility and acceptability of self-injection among adult and adolescent DMPA users; compare method satisfaction rates between patients who self-administer and those who receive in-clinic injections; and compare costs associated with contraceptive care across both groups.

Primary study outcome: DMPA sc continuation at one year by self-report in both the self- and clinic administration arms.

Secondary study outcomes: Patient-reported satisfaction with treatment; satisfaction with home use; cost differentials.

Primary research question: Will allowing for self-administration of DMPA sc outside of the clinic setting result in increased method continuation rates at 6 and 12 months?

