## Secondary research questions:

- Do adult and adolescents patients report that self-administration of DMPA sc is a feasible and satisfactory alternative to clinic administration of DMPA sc?
- What are the cost-related implications of self-administration of DMPA sc compared to clinic administration for patients, providers, and payers?

Primary Hypothesis: We hypothesize higher continuation rates among self-administration users compared to patients who receive in-clinic administration.

- Independent variable: Self-administered DMPA sc versus clinic administered DMPA sc.
- Dependent variables: DMPA continuation rates at 6 and 12 months, defined as having received 3 contraceptive injections by 26 weeks post-enrollment and 4 injections by 42 weeks post-enrollment.

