#### **Number of Subjects and Statistical Power**

The study sites will enroll a combined total N of 400 women. Individuals will be randomized to self-administration or clinic administration with a 1:1 allocation, such that 200 women will be randomized to self-injection, and 200 women to clinic administration. A 15% loss to follow-up rate will yield completed surveys from approximately 340 participants. Based on previous studies, we hypothesize greater continuation rates among self-injection users compared to patients who receive standard care and have sufficient statistical power to detect a difference of 13% or greater. While we will ask subjects about unintended pregnancies, given the high efficacy of DMPA, we will not have statistical power detect a difference between groups.

Given the primary study hypothesis that increased accessibility to DMPA through self-administration will result in higher method continuation rates and the results of prior studies, we estimate that the intervention group will have a 70% continuation rate at 12 months and the control group a 57% continuation rate. With a one-sided  $\alpha$ =0.05 and a  $\beta$ =0.80 and accounting for an approximately 15% dropout rate, completed follow-up from 338 subjects will be sufficient to detect the hypothesized difference. The study is not designed to detect statistically significant differences between adolescents and adults, or between method initiators and continuers.

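### Contacts with survey non-responders only prompt for the survey; without a minimum outcome question, a woman who is reached may still give no primary outcome, mainly in the self-administration arm

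*Combined protocol and SAP*

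**What the plan says.** Objectives and Hypotheses defines the primary outcome as "DMPA sc continuation at one year by self-report in both the self- and clinic administration arms". The primary hypothesis, under Secondary research questions, makes continuation operational: "defined as having received 3 contraceptive injections by 26 weeks post-enrollment and 4 injections by 42 weeks post-enrollment".

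For women who have not returned a survey by 16 weeks after the previous injection, Follow-Up Procedures provides that "study staff will contact the subject twice and at her alternate contact to remind them to complete the survey". The rest of that sentence makes clear that continuers and discontinuers are both to be reminded. It does not tell staff to ask for, or write down, injection status.

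Two provisions in Study Design bear on the gap. On mode: "Follow-up surveys will be conducted at 6 and 12 months via secure email, phone, text messaging, or a combination to increase response rate". On sources: "study outcomes will be ascertained by self-report and medical record review". No section says when a record replaces a missing self-report.

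Number of Subjects and Statistical Power projects that "A 15% loss to follow-up rate will yield completed surveys from approximately 340 participants", against 338 needed. Data Analysis specifies intent-to-treat and gives no rule for a missing outcome.

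**The concern.** The contact is the last planned chance to learn whether a non-responder is still using DMPA, and its only stated purpose is to send her back to a questionnaire she has not completed. If she does not complete it, the plan provides no shorter route to the outcome, although a few questions during the same contact could settle it.

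The two arms are not equally exposed. Clinic injections, including those given after crossover, should appear in the medical record. Under Study Procedures a woman who goes on to self-inject at home takes three doses away with her, and those injections are not given in clinic. The Study Drug Accountability log counts doses dispensed or returned, not doses injected. For her, self-report is in effect the only source.

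The plan already takes a more direct line elsewhere. Under Study Procedures, a new user's missing pregnancy-test result is itself the reason for staff to contact her and log it. The primary outcome has no equivalent.

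At stake are a little power in a trial with almost no slack and, more importantly, how far the estimated difference depends on women whose outcome is unknown.

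**Working it through.** **Inputs.** From Number of Subjects and Statistical Power: 70% versus 57% continuing, one-sided alpha 0.05, 80% power, 200 per arm, 15% loss. The share of the missing women who could be recovered is not in the documents and is assumed below.

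**1. The plan's own figure.** With pooled null variance and no continuity correction,

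n per arm = [z(0.95)·√(2p̄q̄) + z(0.80)·√(p₁q₁ + p₂q₂)]² / d²

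with p̄ = 0.635 and d = 0.13. Here √(2 × 0.635 × 0.365) = 0.6808 and √(0.2100 + 0.2451) = 0.6746. The numerator is (1.6449 × 0.6808 + 0.8416 × 0.6746)² = (1.1199 + 0.5678)² = 2.848. Dividing by 0.0169 gives 168.5, so 169 per arm and 338 in total, as stated. 338/0.85 = 398, close to the 400 planned, and 400 × 0.85 = 340. The expected surplus is two women.

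**2. Power by number of known outcomes.** Power = Φ[(0.13·√n − 1.1199)/0.6746], n per arm. At n = 170 this is Φ(0.852) = 80.3%.

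| Share of the 60 recovered (assumed) | Known outcomes | Power |
|---|---|---|
| 0% | 340 | 80.3% |
| 10% | 346 | 80.9% |
| 20% | 352 | 81.5% |
| 50% | 370 | 83.2% |

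This spreads the loss evenly over the arms. If records filled every clinic-arm gap (an assumption), the starting point would be 170 self versus 200 clinic, with 82.9% power. Recovering half of the 30 missing self-arm women would give 185 versus 200 and 84.4%, a gain of 1.5 points.

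**3. Bounds on the difference.** Let a share m be missing in each arm, and let responders continue at the planned rates. Counting the missing women all against, then all in favour of, self-administration gives 13(1 − m) ± 100m points.

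- m = 0.15 (30 per arm): 11.05 ± 15. In whole women, 119 and 97 continuers among 170 responders per arm: lower 119/200 − 127/200 = −4.0; upper 149/200 − 97/200 = +26.0.
- m = 0.075 (15 per arm): 12.025 ± 7.5, so +4.5 to +19.5.

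The 15 and 7.5 are half-widths around 11.05 and 12.025. They are not shifts from the planned 13 points.

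**4. Why an unequal gap matters (illustration only).** Suppose records fill the clinic arm and the 15% missing in the self arm are counted as discontinued, although all non-responders in fact continue at the planned rates. The comparison becomes 0.70 × 0.85 = 59.5% versus 57%, a difference of 2.5 points. The plan states no such rule, but it states no other either.

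**The case against.** The strongest reply is that the plan is less bare than the single sentence suggests. Surveys may be taken by phone or text, so a staff call can turn into the survey. Records are a second source, and Informed Consent requires permission to review them. Compensation pays $30 and $40 for the two follow-up surveys. Nothing says that a part-completed survey is discarded, and the survey and contact scripts are not in the text available. All of this stands, and it is why the loss is possible rather than certain. It does not close the gap: Follow-Up Procedures does not direct staff to convert the contact, and records cannot show home injections.

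A reader might also infer that the plan counts a woman as followed only if she completes a survey. The documents do not support that. The figure of 340 completed surveys is a sample-size projection, and the next paragraph speaks more generally of completed follow-up. Neither is a rule for ascertaining the outcome.

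Nor are all 60 expected losses recoverable. A different question does nothing for women who are never reached, and the documents do not say how many are reached but silent.

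Finally, one might see a contradiction between two staff contacts here and the purpose given in Study Procedures for the alternate person: "an alternate person to contact if they cannot be reached after several attempts". An emailed survey, two staff contacts and then the alternate can fairly be called several attempts, so no conflict is shown.

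**Conclusion.** The point holds as a cheap improvement in how the primary outcome is collected. The text directs only a reminder, the outcome rests on self-report, and the backstop of clinic records is missing for home doses 2 to 4. The residual loss therefore sits mainly in the self-administration arm and may be differential.

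The power gain is small: from 80.3% to between 80.9% and 83.2% if 10% to 50% of the expected 60 are recovered. Those shares are assumptions, not forecasts. The gain in robustness is larger. With 30 missing per arm the extreme bounds include zero; with 15 they do not. That result assumes that responders continue at the planned rates and that half of the missing women in each arm are recovered.

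It would be wrong to infer that the sample size is in error, since 338 reproduces exactly. It would also be wrong to infer that two contacts will push losses above 15%, as the documents give no basis for that.

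**What to change.** Amend the sentence in Follow-Up Procedures so that, at the planned non-responder contacts with the woman herself at 6 and 12 months, staff first invite the full survey. If it is not completed then, they ask and log a minimum outcome item, worded identically in both arms:

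- the number of DMPA injections received, including the one at enrollment; and
- their dates or, failing that, whether the third was received by week 26 and the fourth by week 42.

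A bare count with the date of the last injection is not enough. It leaves open whether the enrollment injection is included, and for a woman with five injections the last date does not show when the fourth was given.

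State that the answer counts as the self-reported primary outcome whether or not the survey follows, and record the mode so that a sensitivity analysis can separate staff-asked from self-completed answers. The item should go to the woman only, not to her alternate contact.

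The cost is a short form on the existing Qualtrics platform, a line in the call script and a little staff time. There are two downsides. Answers given to staff may be more favourable than those given online, which the mode record lets the analyst examine. A short item may also reduce full-survey completion, and so cost satisfaction and cost data, which is why the full survey is offered first.
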